6.6.3. Vital Signs

Vital sign data will be databased and available upon request.

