3. OBJECTIVES AND ENDPOINTS

Objectives	Endpoints
Primary: 
To estimate the rBA of the nirmatrelvir/ritonavir CCI oral powder mixed with water compared to the nirmatrelvir/ritonavir CCI commercial tablets under fasted conditions.To estimate the rBA of the nirmatrelvir/ritonavir CCI oral powder mixed with infant formula compared to the nirmatrelvir/ritonavir CCI commercial tablets under fasted conditions.To estimate the rBA of the nirmatrelvir/ritonavir CCI oral powder mixed with vanilla pudding compared to the nirmatrelvir/ritonavir CCI commercial tablets under fasted conditions.To estimate the rBA of the nirmatrelvir/ritonavir CCI oral powder mixed with vanilla pudding under fed conditions compared to the nirmatrelvir/ritonavir CCI commercial tablets under fasted conditions.	Primary: 
The test/reference ratios for AUC_{inf} (if data permits), AUC_{last}, and C_{max} of nirmatrelvir and ritonavir.
Secondary: 
To estimate the effect of food on the rBA of the nirmatrelvir/ritonavir CCI oral powder mixed with vanilla pudding.To evaluate the safety and tolerability of nirmatrelvir/ritonavir in healthy participants.To assess the palatability of nirmatrelvir/ritonavir oral powder mixed with water/infant formula/vanilla pudding.	Secondary: 
The test/reference ratios for AUC_{inf} (if data permits), AUC_{last}, and C_{max} of nirmatrelvir and ritonavir.Assessment of TEAEs, clinical laboratory abnormalities, vital signs, PEs, and 12 lead ECGs.Assessment of palatability via questionnaire: mouth feel, bitterness, tongue/mouth burn, throat burn and overall liking.

Objectives	Endpoints
CCI [REDACTED]	[REDACTED]
[REDACTED] [REDACTED]	[REDACTED] [REDACTED]
[REDACTED]	[REDACTED]

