9.3.3. Other Safety Analyses

All safety analyses will be performed on the safety population.

AEs, ECGs, BP, PR, and safety laboratory data will be reviewed and summarized on an ongoing basis during the study to evaluate the safety of participants. Any clinical laboratory, ECG, BP, and PR abnormalities of potential clinical concern will be described. Safety data will be presented in tabular and/or graphical format and summarized descriptively, where appropriate.

Medical history and PE and neurological examination information, as applicable, collected during the course of the study will be considered source data and will not be required to be reported, unless otherwise noted. However, any untoward findings identified on physical

and/or neurological examinations conducted during the active collection period will be captured as AEs, if those findings meet the definition of an AE. Data collected at Screening that are used for inclusion/exclusion criteria, such as laboratory data, ECGs, and vital signs, will be considered source data, and will not be required to be reported, unless otherwise noted. Demographic data collected at Screening will be reported.

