3.5. Safety Endpoints

The following data are considered in standard safety summaries (see protocol for collection days, baseline assessment, and list of parameters):

- adverse events (AE)
- laboratory data
- vital signs data
- electrocardiogram (ECG) results

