5.3.2. Safety Data

Missing values in standard summaries of AEs, laboratory data, vital signs, and ECGs will be imputed according to CaPS.

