6.6. Safety Summaries and Analyses

All safety analyses will be performed on the Safety Analysis Set.

Safety data will be presented in tabular and/or graphical format and summarized descriptively, where appropriate.

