6.6.2. Laboratory Data

Laboratory data will be listed and summarized by treatment in accordance with the CaPS.

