6.6.4. Electrocardiograms

ECG data will be databased and available upon request.

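### The SAP plans no vital-sign or ECG output, which conflicts with its own sections 3.5 and 5.3.2 and with protocol 9.3.3, and SAP 2.1 declares no change

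*SAP*

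**What the plan says.** SAP 6.6.3 consists of one sentence: "Vital sign data will be databased and available upon request". SAP 6.6.4 is its twin: "ECG data will be databased and available upon request".

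Other parts of the plan point the other way:

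- Protocol section 3, repeated in SAP 2.2, gives the secondary safety endpoint as "Assessment of TEAEs, clinical laboratory abnormalities, vital signs, PEs, and 12 lead ECGs".
- Protocol 9.3.3 commits to a description: "Any clinical laboratory, ECG, BP, and PR abnormalities of potential clinical concern will be described".
- SAP 3.5 introduces a list that includes vital signs and ECG results with "The following data are considered in standard safety summaries".
- SAP 5.3.2 sets a rule for missing data: "Missing values in standard summaries of AEs, laboratory data, vital signs, and ECGs will be imputed according to CaPS".
- SAP 6.6 opens with a general statement, shared with protocol 9.3.3: "Safety data will be presented in tabular and/or graphical format and summarized descriptively, where appropriate".
- For laboratory data, SAP 6.6.2 does name outputs: "Laboratory data will be listed and summarized by treatment in accordance with the CaPS".

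SAP 3.5.3 defines a predose baseline in each period for vital signs, and SAP 3.5.4 defines a Period 1 Day 1 predose baseline for ECGs. SAP 2.1 states that there are no modifications to the protocol's analysis plan.

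**The concern.** The two SAP sections that should name the vital-sign and ECG outputs name none, while other sections of the same SAP assume that summaries exist. A programmer cannot tell from the document whether to produce them.

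If 6.6.3 and 6.6.4 are followed as written, these two parts of a secondary endpoint reach the study report only where a finding was recorded as an adverse event. There would be no by-treatment summary of blood pressure and pulse rate. Abnormalities of potential clinical concern that were not recorded as adverse events would go undescribed, although protocol 9.3.3 promises that description.

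Blood pressure is not an incidental measurement here. The risk table in protocol 2.3.1 lists hypertension for nirmatrelvir, citing preclinical increases and a small imbalance in hypertension events in C4671005 (1% against under 1%), and gives vital-sign and adverse-event monitoring as the mitigation. Protocol 4.2 reports that in C4671024 nirmatrelvir Cmax was 61% higher with powder in vanilla pudding than with tablets, so a comparison of blood pressure by treatment has some interest.

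**Working it through.** The main question is one of text; arithmetic serves only to size it.

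**Text comparison**

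| Question | Sections implying an output | Sections planning none |
|---|---|---|
| Are vital signs and ECGs summarised? | SAP 3.5 and SAP 5.3.2 | SAP 6.6.3 and 6.6.4 |
| Are abnormalities of potential clinical concern described? | Protocol 9.3.3, unqualified | SAP 6.6.3 and 6.6.4 name no place for it |
| Are the defined baselines used? | SAP 3.5.3 and 3.5.4 define them | No planned output uses them |
| Is a departure from the protocol declared? | Protocol section 9 permits the SAP to modify the plan | SAP 2.1 declares none |

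The first row is a contradiction inside the SAP and does not depend on how the protocol is read. The second is a conflict with the protocol. It rests on the abnormalities sentence alone, because the general presentation sentence is qualified and the sentence on ongoing review can be read as referring to in-study monitoring.

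**Scheduled readings.** Inputs: 12 participants in 6 sequences of 2 (protocol Table 3); vital signs predose, at 2 h and at 6 h on Day 1 of each of 5 periods and once on Period 5 Day 4; ECG predose on Period 1 Day 1 and on Period 5 Day 4 (protocol section 1.3). Screening and early-termination readings are left out, and all 12 are assumed to complete.

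- Blood pressure and pulse rate, all on-study: 12 × 5 × 3 + 12 = 192.
- Predose baselines: 12 × 5 = 60.
- Post-dose with a same-period baseline: 12 × 5 × 2 + 12 = 132.
- Treatments A, B and C: 12 × 2 = 24 each.
- Treatments D and E: 24 + 6 = 30 each, because sequences 1 to 3 end on E and sequences 4 to 6 end on D, giving 6 Day 4 readings apiece.
- Check: 3 × 24 + 2 × 30 = 132.
- A table at 2 h and 6 h only would use 12 × 5 × 2 = 120 of the 132, or 24 per treatment.
- ECGs: 12 + 12 = 24, of which 12 are post-dose.

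**What the post-dose ECGs can show.** They fall about 72 h after the fifth dose. With the nirmatrelvir half-life of about 6 to 13 h in protocol 4.2, that is 72/13 = 5.5 to 72/6 = 12 half-lives, so they say little about effects near peak concentration.

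**Contrast with laboratory data.** The only scheduled post-dose safety laboratory sample is on Period 5 Day 4, which can follow only D or E. The SAP summarises that by treatment, yet plans nothing for blood pressure and pulse rate, which are measured at 2 h and 6 h after every treatment.

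**The case against.** The strongest reply has four parts.

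1. **The qualifier.** Protocol 9.3.3 and SAP 6.6 promise tables, graphs and descriptive summaries only where appropriate, so omitting tables is within the wording and SAP 2.1 is defensible on that point. This stands for tables. It does not reach the abnormalities sentence, which has no qualifier, or the mismatch between SAP 3.5 and 5.3.2 and SAP 6.6.3 and 6.6.4.
2. **Silence is not prohibition.** Report text written from the database could describe abnormalities. True, but the SAP assigns that task nowhere, and the sections where it belongs state a different plan.
3. **Adverse-event capture.** Physical examinations are in the same endpoint line and are reported only through adverse events; clinically relevant vital-sign and ECG findings are captured that way too. However, protocol 9.3.3 exempts from reporting only history, examination findings and screening data. On-study blood pressure, pulse rate and ECGs are not exempt. Protocol Appendix 8 also lists ECG findings that merely may qualify as adverse events, so that route is narrower than the commitment.
4. **The remedy goes beyond the protocol.** No section promises change from baseline at 2 h and 6 h by treatment, and the documents give no criteria of concern for vital signs. This is fair: the table is a recommendation, and the criteria must come from the sponsor's standards. The ECG part is also of little weight, with one scheduled post-dose tracing per participant.

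**Conclusion.** The concern holds. SAP 6.6.3 and 6.6.4 contradict SAP 3.5 and 5.3.2, and they leave the description promised in protocol 9.3.3 without any output. Protocol section 9 allows the SAP to depart from the outlined analyses, but SAP 2.1 says that it does not.

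As written, no output is assigned to 132 scheduled post-dose blood pressure and pulse rate readings or to 12 post-dose ECGs, assuming 12 completers and the published schedule. These counts measure the data left without an output, not a bias in any result.

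This is a reporting gap in a secondary safety endpoint that should be closed before the analysis. Primary PK estimates are untouched, recorded adverse events are still reported, and 12 participants support description only. The blood pressure and pulse rate part carries most of the weight; the ECG part is minor.

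**What to change.** - **SAP 6.6.3:** summarise supine systolic and diastolic blood pressure and pulse rate by treatment, as value and change from that period's predose reading at 2 h and 6 h. Add counts meeting the sponsor's standard criteria of potential clinical concern, and cite those criteria.
- **SAP 6.6.4:** list or count ECG values of potential clinical concern overall. A table of mean changes is optional, given the timing of the only scheduled post-dose ECG.
- **If the sponsor prefers to omit the summaries:** declare and justify this in SAP 2.1, bring SAP 3.5 and 5.3.2 into line, and state where the description required by protocol 9.3.3 will appear.

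The cost is SAP wording and a few standard outputs from data already due to be collected, with baselines already defined in SAP 3.5.3 and 3.5.4. Study conduct and data collection do not change.

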6.6.4. Electrocardiograms

ECG data will be databased and available upon request.

7. INTERIM ANALYSES

No formal interim analysis will be conducted for this study. As this is an open-label study, the sponsor may conduct unblinded reviews of the data during the course of the study for the purpose of safety assessment, facilitating PK modeling, and/or supporting clinical development.

Final analysis will follow the official database release. As this will be an open-label study, there is no formal unblinding of the randomization code.

PFIZER CONFIDENTIAL

APPENDICES

Appendix 1. SAS Code for Analyses

An example of the PROC MIXED code is provided below:

For primary objectives:

```
proc mixed data=tab.pk;
  class seq period trt participant;
  model l&var=seq period trt/ ddfm=KR;
  random participant(seq) /subject=participant(seq);
  lsmeans trt;
  estimate 'B vs A' trt -1 1 0 0 0 /cl alpha=0.1;
  estimate 'C vs A' trt -1 0 1 0 0 /cl alpha=0.1;
  estimate 'D vs A' trt -1 0 0 1 0 /cl alpha=0.1;
  estimate 'E vs A' trt -1 0 0 0 1 /cl alpha=0.1;

  ods 'Estimates' out=est&var;
  ods 'lsmeans' out=ls&var;
  ods 'covparms' out=cov&var;
  ods 'tests3' out=tst&var;
run;
```

/* Letter assignments for treatments (trt) within the estimate statement above are as follows

A: Single oral dose of nirmatrelvir/ritonavir CCI [REDACTED] tablets under fasted condition (Reference);

B: Single oral dose of nirmatrelvir/ritonavir CCI [REDACTED] oral powder mixed in water under fasted condition (Test);

C: Single oral dose of nirmatrelvir/ritonavir CCI [REDACTED] oral powder mixed in infant formula under fasted condition (Test);

D: Single oral dose of nirmatrelvir/ritonavir CCI [REDACTED] oral powder mixed in vanilla pudding under fasted condition (Test);

E: Single oral dose of nirmatrelvir/ritonavir CCI [REDACTED] oral powder mixed in vanilla pudding under fed condition (Test) */

For secondary objective:

```
proc mixed data=tab.pk;
  where trt in ("D", "E");
  class seq period trt participant;
  model l&var= seq period trt / ddfm=KR;
  random participant(seq) / subject=participant(seq);
  lsmeans trt;
  estimate 'E vs D' trt -1 1 /cl alpha=0.1;
```

```
ods 'Estimates' out=est&var;
ods 'lsmeans' out=ls&var;
ods 'covparms' out=cov&var;
ods 'tests3' out=tst&var;
run;
```

/* Letter assignments for treatments (trt) within the estimate statement above are as follows;
D: Single oral dose of nirmatrelvir/ritonavir **CCI** [REDACTED] oral powder mixed in vanilla
pudding under fasted condition (Reference);
E: Single oral dose of nirmatrelvir/ritonavir **CCI** [REDACTED] oral powder mixed in vanilla
pudding under fed condition (Test) */

CCI [REDACTED]

Appendix 2. List of Abbreviations

Abbreviation	Term
%CV	coefficient of variation
AE	adverse event
AUC _{inf}	area under the concentration-time curve from time 0 to infinity
AUC _{last}	area under the concentration-time curve from 0 to time of last measurable concentration
BLQ	below the limit of quantitation
BP	blood pressure
CaPS	Clinical Data Interchange Standards Consortium and Pfizer Standards
CI	confidence interval
C _{last}	estimated plasma concentration at the last quantifiable time point estimated from the log-linear regression analysis
C _{max}	maximum observed plasma concentration
CSR	clinical study report
ECG	electrocardiogram
HR	heart rate
k _{el}	the terminal phase rate constant calculated by a linear regression of the loglinear concentration-time curve
LLQ	lower limit of quantitation
mg	milligram
N/A	not applicable
NC	not calculated
ND	not done
NS	no sample
PK	pharmacokinetic(s)
PR	pulse rate
QRS	Combination of Q-, R- and S- wave on an electrocardiogram representing ventricular depolarization
QTc	corrected QT
QTcF	corrected QT (Fridericia method)
RR	respiratory rate
SAP	statistical analysis plan
SD	standard deviation
SoA	schedule of activities
C	[REDACTED]
CI	[REDACTED]
TEAE	treatment emergent adverse event
CCI	[REDACTED]
